5.3.2. Dosing Instructions

The methodology will be detailed in the Pharmacy Manual.

On the days of IMP dosing:

Inhaled RESP301 nebulisation:

- all treatment regimens:
 - each dose is to be given using freshly prepared admix solution i.e., inhalation of the RESP301 should start with [REDACTED]
 - on Day 1 only: a short acting beta agonist is to be administered before starting the nebulisation for each dose, within 30 minutes of RESP301 is suggested
 - inhalation of RESP301 should be completed within [REDACTED] of starting NEB, pauses may be taken during NEB if not tolerated. The NEB should be stopped during a pause to preserve the remaining IMP until restarted.
 - the first dose should be given in the morning
 - All dosing should occur at approximately the same time each day (window of \pm 1 hour of the IMP dose/s on Day 1).
- once or twice daily:
 - When dosing overlaps with overnight sputum sample collection, sputum collection should be paused during and for [REDACTED] the end of the neb. A cup ([REDACTED] [REDACTED]) of water should be taken after the neb is complete, and prior to continuation of overnight sputum sample to wash away any remaining RESP301 from the airway.
 - the first dose should be given at half dose (half of each vial)
- three times a day (alone or with HRZE):
 - the first 2 doses should be given at half dose (half of each vial)
 - this tds dosing will be [REDACTED] to prevent overnight disruption to participants and limit overlap of dosing and sputum sampling
- twice or three times a day (alone or with HRZE):
 - to ensure a dose does not affect any *M.tb* present in the overnight sputum sample, should a dose overlap with the overnight sample collection window, sputum collection is

to be paused for [REDACTED] completion of inhalation of the RESP301 dose. Should the participant need to expectorate sputum during this pause, this will occur into a separate container which will be destroyed. The participant is to drink a cup ([REDACTED]) of water after the neb is complete, and prior to continuation of overnight sputum sample collection

HRZE oral dosing (alone or with RESP301):

- to occur in the morning
- preferably with a full glass of water fasted [REDACTED] However, if gastrointestinal irritation occurs, the tablets may be taken with food.
- if aluminium containing antacids are taken, administer one hour after the HRZE tablet/s dose.

HRZE plus RESP301 three times a day

- RESP301 tds instructions and the HRZE instructions above to apply.
- oral dose of the HRZE should be given in the morning, followed within [REDACTED] the start of the first (morning) dose of inhaled RESP301.

The exact dosing times (start time and end time) of each individual IMP will be recorded.

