	
6. Rifampicin susceptible pulmonary TB as determined by molecular testing.7. Ability to produce an adequate volume of sputum as estimated from a pre-treatment overnight sputum collection sample (estimated 10 mL or more).8. A chest X-ray taken during the screening period or up to 2 weeks before screening which, in the opinion of the investigator, is consistent with pulmonary TB.9. Spirometry performed during screening with a Forced Expiration Volume in the first second (FEV1) of $\geq 40\%$.10. Be of non-childbearing potential or willing to use effective methods of contraception, as defined in section 4.3.4.
	
Exclusion Criteria
 
Participants will be excluded from participation if they fulfil any of the following criteria.

	
Medical History:
 
1. Evidence of clinically significant conditions or findings, other than TB, that might compromise safety or the interpretation of study endpoints, per discretion of the investigator.2. Clinical evidence of extra-thoracic TB, that might compromise safety or the interpretation of study endpoints, per discretion of the investigator.3. History of allergy to any of the study IMP as confirmed by the clinical judgement of the investigator.4. Alcohol or drug abuse, that in the opinion of the investigator, is sufficient to compromise the safety or cooperation of the participant.5. HIV positive AND:
(a) CD4 < 350 cells/mm³(b) OR are receiving antiviral therapy (ART).6. Methaemoglobin saturation (SpMet) $>3\%$.7. Female participant who is pregnant or breast-feeding.8. Participants planning to conceive a child within the anticipated period of study participation and for at least 90 days after the last dose of IMP in the study.
	
Treatment History
 
9. Participation in other clinical studies with investigational agents within 8 weeks prior to screening.10. Treatment received for this episode of TB with any drug active against M.tb [fluoroquinolones (including moxifloxacin, levofloxacin, ofloxacin and ciprofloxacin), bedaquiline, pretomanid, delamanid, ethionamide, isoniazid, ethambutol, amikacin, cycloserine, rifabutin, rifampicin, streptomycin,

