2.2.3.1. RESP301 development program

- [REDACTED]
- [REDACTED]
- [REDACTED]
- [REDACTED]

Table 8: RESP301 Clinical Studies

Study	Status	Title	No of participants receiving at least 1 dose of RESP301	Comment
RESP301-005 (CORVIS)	Completed	Phase 2 study, entitled, "Community patients at Risk of Viral Infections including SARS-CoV-2".	39	Single ascending dose study
RESP301-003 (NOMab)	Ongoing	Phase II, open label single centre study assessing the efficacy, safety and tolerability of RESP301, a nebulized nitric oxide generating solution, in patients with M. abscessus -pulmonary disease	5	
RESP301-007 (PROTECT-Surg)	Ongoing	A Phase 2, Platform, Randomized Clinical Study entitled, "Preventing pulmonary complications in surgical subjects at risk of COVID-19".	79	
RESP301-002 - NOCOv2	Terminated early	An open-label, adaptive randomized, controlled multicentre study to evaluate the efficacy and safety of RESP301+SOC vs SOC in hospitalized participants with COVID-19 WHO grade 3&4.	14	Early terminated due to changes in the standard of care during the study and limited patient availability
RESP301-006 (PREVENT)	Terminated early	Phase 2/3 study, entitled, "Prevent Viral Exposure and Transmission study: a SARS-CoV-2 PEP Study"	0	Whilst approved by the Ethics Committee and Regulatory Authority, was never initiated due to lower than anticipated numbers of patients meeting the eligibility criteria

As of 30 March 2023, a total of 175 AEs have been reported in 51 patients across the RESP301 development programme, of which 60 were deemed highly probably related to RESP301. Of note 52 (87%) of these AEs were reported in RESP301-005 (CORVIS study) in patients with COPD/Bronchiectasis with cough being the most frequently reported AE in this group.

RESP301 has been generally well tolerated, but there appears to be a small sub-population of patients, notably Chronic Obstructive Pulmonary Disease (COPD) patients with airway hyperresponsiveness complicated by very poor underlying respiratory function (FEV1 less than 30% of predicted) who may be at increased risk of AEs (specifically bronchoconstriction). This appears to be rapidly reversed with short acting bronchodilators (SABA) and may be prevented by pre-dosing with a SABA, as demonstrated in the Single Ascending Dose portion of the CORVIS study. Given this, patients with a FEV1 of less than 40% prior to dosing with the IMP will be excluded from this study.

In addition:

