4.3.3. Concomitant Medications and Procedures

Concomitant Medication and Procedures are defined as any medication taken/procedure performed within 14 days prior to first dose of IMP and during the study until the follow-up visit (all participants including early withdrawal/discontinuations). This includes for new and/or worsening medical conditions.

Concomitant medications should be kept to a minimum during the study. However, if necessary for the participant's welfare and are unlikely to interfere with the IMP, they may be given at the discretion of the investigator once the prescribing information has been consulted and reviewed carefully. The determinations listed in the respective contraindicated, warning, and precaution sections must be respected to prevent any potentially serious and/or life-threatening drug interactions. Drugs that may cause methaemoglobinemia may be used with caution.

The following concomitant medications are prohibited throughout the study. Please confirm any medication you are uncertain of with the Medical Monitor.

- [REDACTED]

Concomitant medications and procedures are to be reported on the concomitant medication and procedures page of the electronic case report form (eCRF). For concomitant medication the reported information is to include the drug name (trade name if known, otherwise generic), treatment period, dosing regimen, route of administration, and its indication (diagnosis if known, otherwise separate symptoms). Any changes in the dosage of concomitant medication must also be reported on the concomitant medication page of the eCRF. The corresponding diagnosis should be completed as medical history (before first dose of IMP) or as an AE (at or after first dose of IMP).

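### Bronchodilator pre-dosing runs by calendar day and the half-dose lead-in by dose number, so only the once-daily arm takes its first full RESP301 dose outside the pre-dosing rule

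*Protocol*

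**What the plan says.** Protocol section 5.3.2 (Dosing Instructions) holds two start-up rules for RESP301.

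- **SABA rule, all regimens:** "on Day 1 only: a short acting beta agonist is to be administered before starting the nebulisation for each dose". A timing within 30 minutes of RESP301 is suggested.
- **Half-dose rule, by schedule:** for once or twice daily, "the first dose should be given at half dose (half of each vial"; for three times a day, alone or with HRZE, "the first 2 doses should be given at half dose (half of each vial". The tds instructions apply unchanged to the combination arm.

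Section 2.2.3.1 gives the background. It describes a small group of patients, notably COPD patients with airway hyperresponsiveness and FEV1 below 30% of predicted, "who may be at increased risk of AEs (specifically bronchoconstriction". It adds that this appears to be rapidly reversed by a SABA and "may be prevented by pre-dosing with a SABA, as demonstrated in the Single Ascending Dose portion of the CORVIS study". The entry limit follows from that: "Given this, patients with a FEV1 of less than 40% prior to dosing with the IMP will be excluded from this study". The matching inclusion criterion is in the Synopsis (section 1.1): "Spirometry performed during screening with a Forced Expiration Volume in the first second (FEV1") of 40% or more.

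No visible text extends the SABA beyond Day 1 for qd or says why it stops before the step to full dose.

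**The concern.** The start-up has two protections, a reduced dose and a bronchodilator. In bd and tds they are withdrawn one at a time: the participant first takes the full dose with SABA cover and loses the cover the next day. In qd both are withdrawn at the same administration, because one rule counts days and the other counts doses. Tolerating a half dose under a bronchodilator is weak evidence that a full dose without one will be tolerated.

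What is at stake is bronchoconstriction at the step-up, the event that the protocol itself says pre-dosing may prevent. The FEV1 limit removes the worst lung function, but anyone from 40% upward is eligible. No listed exclusion names COPD or airway hyperresponsiveness; these are left to investigator discretion. Some residual risk is therefore plausible, although the documents give no rate for it. Safety and tolerability of qd, bd and tds dosing is the secondary objective in section 3.3.2.

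**Working it through.** The plan gives no figure of its own here, so the check is to lay out the schedule.

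**Inputs**
- Doses per day, m: qd 1, bd 2, tds 3, for 14 days (section 5.1).
- Half doses at the start, h: 1 for qd and bd, 2 for tds with or without HRZE (section 5.3.2).
- SABA required before each Day 1 dose only (section 5.3.2).
- The first dose of the day is in the morning (section 5.3.2), so all m doses fit on Day 1.
- About 15 participants per RESP301 arm (section 4.1).
- All scheduled doses are assumed taken.

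**Formulas**
- First full dose number = h + 1.
- Day of first full dose = floor(h / m) + 1. It is covered only if this is Day 1.
- Total doses = 14m; full doses = 14m − h.
- Full doses under cover = max(0, m − h).
- Covered share of all doses = m / 14m.

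**Results**

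| Schedule | m | h | First full dose | Day | Covered? | Full doses covered / all full doses | Covered / all doses |
|---|---|---|---|---|---|---|---|
| qd | 1 | 1 | dose 2 | floor(1/1) + 1 = 2 | no | 0 / 13 | 1 / 14 = 7.1% |
| bd | 2 | 1 | dose 2 | floor(1/2) + 1 = 1 | yes | 1 / 27 | 2 / 28 = 7.1% |
| tds | 3 | 2 | dose 3 | floor(2/3) + 1 = 1 | yes | 1 / 40 | 3 / 42 = 7.1% |
| tds + HRZE | 3 | 2 | dose 3 | floor(2/3) + 1 = 1 | yes | 1 / 40 | 3 / 42 = 7.1% |

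Planned participants whose first full dose lies outside the SABA rule: 15 of 15 in qd, and 0 of 15 in each of bd, tds and tds + HRZE.

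**Checks on the reading**
- The half-dose instruction must mean the first dose of the study. If it meant the first dose of each day, qd would never reach the 6 mL dose.
- If a bd or tds participant misses a Day 1 dose, the first full dose also moves to Day 2. That is a deviation from the schedule; in qd it is the schedule.
- The word suggested most naturally qualifies the 30-minute timing. If it softens the whole SABA instruction, the mismatch between arms remains.

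**Under the proposed rule** (cover up to and including the first full dose): qd doses 1 and 2 are covered, so 1 of 13 full doses has cover. bd and both tds arms do not change. Extra SABA doses = 1 × 15 = 15.

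**The case against.** The schedule itself is hard to dispute; the case against is about its importance.

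- **The harm is inferred.** Section 2.2.3.1 ties bronchoconstriction to a small group with FEV1 below 30% of predicted, answers it with the 40% limit, and notes rapid reversal with a SABA. Nothing visible says that the SABA was meant to cover the step-up and not simply the first day. This stands, and it keeps the point small.
- **A calendar-day rule can be defended.** In full-dose equivalents, Day 1 delivers 0.5 in qd, 0.5 + 1 = 1.5 in bd and 0.5 + 0.5 + 1 = 2.0 in tds, so the rule covers the heavier first days. In all four arms the first full dose without cover falls on Day 2. That is true, but only qd reaches it with no covered full dose before it.
- **Other safeguards exist.** Participants are inpatients, staff stay with them throughout nebulisation (section 5.3.3), and pauses are allowed. Before qd opens, 15 Stage 1 tds participants will have taken up to 39 uncovered full doses each (15 × 39 = 585). SAP section 9 also names bronchospasm in a trigger for considering an amendment. These limit the harm and give useful evidence. However, each tds participant takes a covered full dose first, so Stage 1 does not test the qd step. Attendance manages an event, whereas pre-dosing is meant to prevent it.
- **Unseen text.** The Pharmacy Manual is not available and parts of the dose rationale, the listed risks and the prohibited-medication list are blacked out. The visible text does not bar a discretionary SABA on Day 2. The finding is therefore that pre-dosing is not required, not that it would be withheld.
- **The fix ends the equal covered share.** qd would go from 1/14 (7.1%) to 2/14 (14.3%), and its first uncovered full dose would move to Day 3. The difference is one bronchodilator dose, which is a trivial cost.

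**Conclusion.** The concern holds. Under section 5.3.2 as written, qd is the only RESP301 schedule whose first full dose lies outside the required SABA cover, and this applies to all of its roughly 15 planned participants. It is a minor inconsistency in airway safety and early tolerability at the step to full dose.

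It does not reach the EBA comparison, since the covered share is 7.1% in every arm. It does not reach the Stage 1 decision, since there is no qd arm in that stage. Nor does it show a bias in whole-period TEAE incidence, since every RESP301 arm takes uncovered full doses from Day 2.

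The count is firm, given full Day 1 dosing and the plain reading of the two rules. How much harm could follow cannot be sized from the documents; it rests on some residual bronchoconstriction risk at FEV1 of 40% and above.

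**What to change.** Before Stage 2 opens, reword the SABA bullet in section 5.3.2 along these lines: *give a short-acting beta agonist before every Day 1 dose, and before any later dose up to and including the first full dose*. Keep the suggested 30-minute timing. If the Pharmacy Manual repeats the rule, change it there too. The recruitment pause after Stage 1 is a natural time to do this.

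The cost is one line of protocol text and one SABA dose on Day 2 for about 15 qd participants; bd and both tds arms are unaffected. No new eCRF field is needed. Concomitant medication is already captured under section 4.3.3 ("For concomitant medication the reported information is to include the drug name", with treatment period and regimen), and section 5.3.2 already has the exact start and end times of each IMP dose recorded.

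If the sponsor intends the SABA to cover the first day only, one sentence in section 5.3.2 giving the reason for qd would also settle the point.

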5.3.3. Participant Compliance

The IMP will be administered and compliance checked by the investigator/designated site personnel. This process will be detailed in the Pharmacy Manual. Where applicable the following checks will occur:

RESP301 nebulisation:

- the participant identity matches the dispensed vials
- the number of RESP301 vials (A and B) before and after mixing and nebulisation
- the date and time of preparation of the nebuliser solution (start and stop)
- the date and time of inhalation of the nebulisation solution (start and stop)
- confirmation the nebuliser is empty/minimal solution remains when nebulisation is complete.
- The investigators or appropriately trained delegated study personnel will remain with the participant whilst they are being nebulised to observe correct administration and monitor SpMet.

HRZE tablets:

- Participants will be checked for IMP compliance by the investigators or study personnel via the hand-and-mouth procedure. Both the hand and mouth of the participant will be checked to ensure that the participant has swallowed the IMP.

This information will be recorded in the participant's source documents and eCRF where required. All packaging will be checked to ensure complete administration.

Table 17 contains guidelines on how to manage HRZE dosing for a participant experiencing vomiting.

[REDACTED]	[REDACTED]
[REDACTED]	[REDACTED]

Please consult the study medical monitor for guidance, caution should be given when considered repeat dosing. This is to be documented in source and in the eCRF.

5.3.4. Manufacturing, Packaging and Labelling

5.3.5. Storage

RESP301 vials will be stored within a temperature range of [REDACTED] °C. [REDACTED]

HRZE will be stored at or below a temperature of 25 °C, in well-closed containers, and protected from light.

All investigational products will be kept securely stored by the site pharmacist/registered dispenser in a secured temperature-controlled area with limited access to designated site personnel only. Only qualified personnel will undertake the preparation, handling and safe disposal of investigational products. Logs will be kept for drug accountability (chain of custody) and temperature.

5.4. Dispensing and Accountability

The site pharmacist/delegated dispenser will be responsible for dispensing the IMP. The IMP will be prepared separately from drugs used for other participants and studies to prevent cross-contamination. Accurate accountability and participant identification records will be kept by the site to assure that the IMP will not be dispensed to any person who is not a participant under the terms and conditions set forth in this protocol i.e., delivery to site, inventory at site, use by participant, destruction etc. The investigator/designee will immediately inform the Sponsor of any quality issues arising with respect to the IMP. The Sponsor will take whatever action is required should such a situation arise. The investigator undertakes to use the study medication only as indicated in this protocol.

5.5. Returns and Destruction

Upon completion or termination of the study, and after IMP accountability and monitoring thereof has been completed, all unused and/or partially used:

- RESP301 will be destroyed by the site according to their standard operational procedure or returned to the sponsor for use or destruction per their standard operational procedure.

- HRZE will be stored for future use or donated where possible.
If no supplies remain, this fact will be indicated in the drug accountability section of the final report.

6. Study Assessments

6.1. Demographic and Baseline Assessments

The demographic and baseline assessments (Table 18) will be performed at the time points described in the study flow chart. Where applicable, sample collection, handling and testing will be described in the Laboratory Manual.

6.2. Activity Assessments

The activity assessments (Table 19) will be performed at the time points described in the study flow chart.

Topic	Percentage
Global warming	98
Evolution	95
Black holes	75
Big Bang theory	65
Quantum mechanics	92
Relativity	90
Neuroscience	88
Climate change	93
Artificial intelligence	91
Neuroscience	89
Neuroscience	87
Neuroscience	85
Neuroscience	83
Neuroscience	81
Neuroscience	79
Neuroscience	77
Neuroscience	75
Neuroscience	73
Neuroscience	71
Neuroscience	69
Neuroscience	67
Neuroscience	65
Neuroscience	63
Neuroscience	61
Neuroscience	59
Neuroscience	57
Neuroscience	55
Neuroscience	53
Neuroscience	51
Neuroscience	49
Neuroscience	47
Neuroscience	45
Neuroscience	43
Neuroscience	41
Neuroscience	39
Neuroscience	37
Neuroscience	35
Neuroscience	33
Neuroscience	31
Neuroscience	29
Neuroscience	27
Neuroscience	25
Neuroscience	23
Neuroscience	21
Neuroscience	19
Neuroscience	17
Neuroscience	15
Neuroscience	13
Neuroscience	11
Neuroscience	9
Neuroscience	7
Neuroscience	5
Neuroscience	3
Neuroscience	1

6.3. Safety and Tolerability Assessments

The safety and tolerability assessments (Table 20) will be performed at the time points described in the study flow chart.

[REDACTED]	[REDACTED]
	[REDACTED] [REDACTED] [REDACTED] [REDACTED] [REDACTED] [REDACTED] [REDACTED]
[REDACTED] [REDACTED] [REDACTED]	[REDACTED] [REDACTED]
[REDACTED]	[REDACTED]

7. Adverse Events

The investigators are responsible for eliciting adverse events by observing the participant and recording all adverse events observed or reported by the participant during the study.

7.1. Definitions

Adverse Event (AE)

Any untoward medical occurrence in a patient or clinical investigation participant administered a pharmaceutical product and which does not necessarily have a causal relationship with this treatment. An adverse event can therefore be any unfavourable and unintended sign (including an abnormal laboratory finding), symptom, or disease temporally associated with the use of a medicinal product, whether or not related to the medicinal product.

Examples of AE include (but are not limited to): clinically significant abnormal test findings, clinically significant symptoms and signs, clinically relevant changes in clinical examination findings, hypersensitivity, progression / worsening of pre-existing condition or underlying disease, recurrence of pre-existing condition, complication and termination of pregnancy.

The criteria for determining whether an abnormal objective test finding should be reported as an AE are follows:

- Test result is associated with accompanying symptoms
- Test result requires additional diagnostic testing or medical / surgical intervention
- Test result leads to a change in study dosing or discontinuation from the study, significant additional concomitant drug treatment, or other therapy
- Test result is considered to be an AE by the Investigator or Sponsor

Repeating an abnormal test, in the absence of any of the above conditions, does not constitute an AE. Any abnormal test results that are determined to be errors do not require reporting as AEs.

An AE does not include the following:

- Medical or surgical procedures performed; the condition that led to the procedure may be an AE if applicable.
- Pre-existing medical condition, condition or laboratory abnormalities present or detected before the IMP first dose that do not worsen. If clinically significant these should be documented in the medical history page of the eCRF.

Serious Adverse Event (SAE)

Any untoward medical occurrence that at any dose:

- results in death
- is life threatening (any event in which the participant was at risk of death at the time of the event; it does not refer to an event, which hypothetically might have caused death if it were more severe)
- requires inpatient hospitalization or prolongation of existing hospitalization (excludes hospitalisation in EBA unit for study purposes unless this is extended due to an AE)
- results in persistent or significant disability/incapacity
- is a congenital anomaly/birth defect
- is a medically important event.

Note: Medical and scientific judgment should be exercised in deciding whether an AE is a medically important event that may not be immediately life-threatening or result in death or hospitalization but may jeopardize the participant or may require medical or surgical intervention to prevent one of the outcomes listed above. Examples of such events are intensive treatment in an emergency room or at home for allergic bronchospasm, blood dyscrasias or convulsions that do not result in hospitalization, or the development of drug dependency or drug abuse. A “suspected transmission of infectious agent by a medicinal product” is also considered a serious adverse event under the SAE criterion “Other medically important condition”.

Adverse Drug Reaction (ADR)

An ADR is defined as a response to a medicinal product which is noxious and unintended at any dose and that is considered causally related (possible, probable, or certain) to an investigational medicinal product. A serious ADR (SADR) is an ADR which meets the serious criteria.

Unlisted (Unexpected) Adverse Event

An adverse reaction, the nature or severity of which is not consistent with the applicable product information (e.g., Investigator's Brochure for an unapproved investigational product or package insert/summary of product characteristics for an approved product). Expectedness is assessed by the sponsor/sponsor's delegate.

Attribution/Causality

The definitions for rating attribution/causality will be as described in Table 21.

Table 21: Adverse Events Attribution/Causality Ratings

Relatedness Rating	Definition
Not Related	An adverse event, which is not related to the use of the drug.

Relatedness Rating	Definition
Unlikely	An adverse event for which an alternative explanation is more likely, e.g., concomitant drug(s) or concomitant disease(s), and/or the relationship in time suggests that a causal relationship is unlikely.
Possible	An adverse event, which might be due to the use of the drug. An alternative explanation, e.g., concomitant drug(s) or concomitant disease(s), is inconclusive. The relationship in time is reasonable; therefore, the causal relationship cannot be excluded.
Probable	An adverse event, which might be due to the use of the drug. The relationship in time is suggestive, e.g., suspicion strengthened by onset of symptoms associated with initiation of drug and/or improvement of symptoms when stopping drug. An alternative explanation is less likely, e.g., concomitant drug(s) or concomitant disease(s).
Certain	An adverse event, which is listed as a possible adverse reaction and cannot be reasonably explained by an alternative explanation, e.g., concomitant drug(s) or concomitant disease(s).

Severity

Severity rating is to be made per the CTCAE Toxicity Table Version 5 dated 27 November 2017 (Appendix 1). For abnormalities NOT found in the toxicity tables, the scale described in Table 22 is to be used to estimate grade of severity.

Table 22: Adverse Event Severity Ratings

Grade	Severity Rating	Definition
Grade 1	Mild	Transient or mild discomfort (< 48 hours); no medical intervention/therapy required.
Grade 2	Moderate	Mild to moderate limitation in activity - some assistance may be needed; no or minimal medical intervention/ therapy required.
Grade 3	Severe	Marked limitation in activity, some assistance usually required; medical intervention/therapy required, hospitalizations possible.
Grade 4	Potentially Life-threatening	Extreme limitation in activity, significant assistance required; significant medical intervention/therapy required, hospitalization or hospice care probable.

Action taken and outcome

The investigator will record the actions taken with the IMP for each AE using the descriptions in Table 23.

Table 23: Adverse Events Action taken with Investigational Medicinal Product

Action Taken	Definition
IMP withdrawn	Participant is permanently withdrawn from the IMP
IMP interrupted	IMP is temporarily withdrawn
IMP unchanged	No action is taken regarding the IMP
Unknown	It is not known what action was taken with the IMP

Action Taken	Definition
Not Applicable	The IMP treatment has been completed prior to reaction /event, or the participant has died
IMP: Investigational Medicinal Product	

The investigator will record the other actions taken, the outcome and the occurrence for each AE using the following descriptions:

Other Action Taken

- none
- medication given
- hospitalisation or prolongation of hospitalisation
- therapeutic or diagnostic procedure.

Outcome

- recovered / resolved
- recovering / resolving
- not recovered / not resolved
- recovered / resolved with sequelae
- fatal
- unknown.

Occurrence

- once
- intermittent
- continuous.

